2.0. INTRODUCTION

2.1. Background and Significance

2.1.1. Clinical Features and Epidemiology of ALS

Amyotrophic lateral sclerosis is a rare degenerative disorder of large motor neurons of the cerebral cortex, brain stem and spinal cord that results in progressive wasting and paralysis of voluntary muscles [1]. The incidence of ALS is currently approximately 2/100,000/year [2, 3] and may be increasing [4]. The lifetime ALS risk is 1 in 600 to 1 in 1000. Fifty percent of people diagnosed with ALS die within three years of onset of symptoms and 90% die within five years [5]. The median age of onset is 55 years. The cause in most cases is unknown. Age and gender are the only risk factors repeatedly documented in epidemiological studies [6]. There is a slight male predominance (3:2 male to female ratio) in sporadic ALS. No treatment prevents, halts or reverses the disease, although riluzole use is associated with a slight prolongation of survival [7, 8].

Essential features of ALS are progressive signs and symptoms of lower motor neuron dysfunction (atrophy, cramps, and fasciculations) associated with corticospinal tract signs (spasticity, enhanced and pathological reflexes) in the absence of sensory findings. There is relative sparing of eye movement muscles and the urinary sphincters. The course is relentless with declines in strength, respiratory function and overall muscle function during the active phase of the disease. Natural history studies have determined that age at onset, site of onset, delay from first symptom to diagnosis, and rate of change in respiratory function are significant predictors of survival.

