7.2.8. Assessment of Muscle Cramps and Fasciculations

The effects of mexiletine on muscle cramps will also be assessed as a secondary endpoint. Cramps in SALS patients are common and are often debilitating. Various medications including quinine sulfate, magnesium, lioresal, dantrolene, clonazepam, diphenylhydantoin and gabapentin, have been used in the treatment of cramps in ALS, though few have been studied in the ALS population and none have clearly shown efficacy. Mexiletine has been shown to have a beneficial impact on muscle cramps in a small non-randomized study of patients with Machado-Joseph disease [45] but has never been studied in ALS patients until the recent safety and tolerable study using mexiletine.

The visual analog scale (VAS) is a scale that measures pain associated with muscle cramping. It will be used to measure muscle cramping in this study. The scale rating is from 0-10; 0 equals no symptoms, 10 equals most severe symptoms. The VAS will be explained at the Baseline visit to all subjects. It will then be completed each day by the subject and entered on a muscle cramps and fasciculations diary. At baseline, subjects will be asked to recount the number and intensity on VAS of muscle cramps experienced in the previous 7 and 30 days. At each visit (beginning at the Week 4 Visit), the coordinator will review the Muscle Cramp/Fasciculations Diary and complete a Muscle Cramp CRF based on this data and/or subject's verbal self-report. Cramp intensity as assessed by a VAS is the most common measure used in cramp trials [44].

Fasciculations will also be recorded in the diary on a daily basis, graded in the following manner: 0. no fasciculations on this day; 1. fasciculations after exertion only, not substantially interfering with daily activity; 2. fasciculations at rest or after exertion, not substantially interfering with daily activity; and 3. fasciculations at rest or after exertion and substantially interfering with daily activity. At baseline, subjects will be asked several questions related to their fasciculations experienced in the previous 14 days. Subjects will be provided with a muscle cramps and fasciculations diary to record muscle cramp frequency and intensity and severity of

fasciculations at home daily. At each subsequent visit, the coordinators will review the diary and record the daily frequency and maximal intensity of muscle cramps and fasciculations before returning the diary or providing the subject with a new diary.

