3.3.7 Fasciculations

Data on muscle fasciculations are captured at baseline by retrospective report of the prior 14-day interval. Data are captured on the experience of any fasciculations, the average duration of fasciculations, the association of fasciculations with exertion or times of rest, the degree to which fasciculations interfere with daily activities, and interference of fasciculations with sleep. Prospective data on fasciculations are recorded starting at baseline by participants in daily diaries and then summarized as weekly summaries indicating the number of days with no fasciculations, with fasciculations after exertion that did not substantially interfere with daily activities, with fasciculations at rest or after exertion that did not substantially interfere with daily activities, and fasciculations that substantially interfered with daily activities.

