3.6 Baseline Characterization

Each analysis sample will be summarized overall and by treatment group for the following characteristics: randomization site; age, sex, race, ethnicity, El Escorial diagnosis, years since ALS symptom onset, delay between symptom onset and ALS diagnosis, site of ALS symptom

onset, use of riluzole at baseline, ALSFRS-R total score, SVC, APB muscle strength by HHD on the dominant hand, TMS parameters, TTNCS parameters, cramping frequency, cramping pain, fasciculation intensity, fasciculation interference with daily living, fasciculation interference with sleep, and RAND-36 physical and mental summary scores. The magnitude of differences between treatment groups will be summarized using Fisher's exact tests for nominal variables and two-sample t-tests for approximately continuous variables. Note that the p-values yielded by these tests do not estimate the probability that the observed differences are due to chance (which is 1 axiomatically).

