3.7.3 Secondary Endpoints

Continuous secondary pharmacodynamic and exploratory clinical and quality of life endpoints will be analyzed using the same analysis samples and models as specified for the primary pharmacodynamic endpoint in Sections 3.7.1 and 3.7.2. Variables that are strongly right-skewed (e.g., maximum MEP amplitude) will be log-transformed prior to analysis, and estimates will be back-transformed for reporting.

Weekly cramping frequency data will be analyzed in similar generalized mixed models treating the number of cramps experienced in a week as a negative binomial random variable with log link and with the log of the number of days at risk for cramps as an offset. Similarly, weekly number of days with fasciculations will be analyzed in similar generalized mixed models treating the number of days with fasciculations in a week as a binomial random variable with logit link. Because diary data are only collected after baseline, fixed effects in the model will include treatment group, post-baseline week, and baseline retrospective report of number of cramps experienced in the prior 30-day interval or the experience of fasciculations in the prior 14-day interval.

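### The days-with-fasciculations model adjusts only for what reads as a yes/no baseline item; adding a baseline grade from items already collected would probably gain a little precision at almost no cost

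*SAP*

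**What the plan says.** SAP 3.7.3 analyses the diary outcome by "treating the number of days with fasciculations in a week as a binomial random variable with logit link", in a generalized mixed model. The shared-baseline approach of the primary analysis is not available here, and the SAP gives the reason: "Because diary data are only collected after baseline, fixed effects in the model will include treatment group, post-baseline week". The remaining fixed effect is a retrospective baseline report. For cramps this is a count over 30 days. For fasciculations it is "or the experience of fasciculations in the prior 14-day interval".

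SAP 3.3.7 lists what the baseline assessment collects: "Data are captured on the experience of any fasciculations, the average duration of fasciculations, the association of fasciculations with exertion or times of rest", followed by "the degree to which fasciculations interfere with daily activities, and interference of fasciculations with sleep". Protocol 7.2.8 agrees in outline: "At baseline, subjects will be asked several questions related to their fasciculations experienced in the previous 14 days". That protocol section also defines the daily diary grade: 0 for none; 1 for after exertion only without substantial interference; 2 for at rest or after exertion without substantial interference; 3 for substantial interference.

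Baseline fasciculation data have other planned uses. SAP 3.6 tabulates "fasciculation intensity, fasciculation interference with daily living, fasciculation interference with sleep" by treatment group, and SAP 3.7.5 correlates baseline fasciculation frequency and interference with TTNCS parameters.

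**The concern.** With no diary before the first dose, baseline adjustment for between-patient differences rests on a single retrospective item. The wording of SAP 3.7.3 matches only the first item in SAP 3.3.7, whether any fasciculations occurred, so the natural reading is a yes/no covariate. It separates patients with no fasciculations from everyone else and says nothing about differences among those who have them. The cramp model in the same paragraph gets a count and so is better served.

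The exertion/rest and interference items cover the same dimensions as the diary's 0-3 grade. If a patient's baseline grade predicts how many diary days will show fasciculations, leaving it out keeps avoidable variance in the treatment comparison. With about 20 patients per arm, that could matter for the width of the interval.

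**Working it through.** **The plan's own figures.** The documents give no power or precision figure for fasciculations. The only efficacy sizing (SAP 3.4) is for RMT, and it reproduces. With 10% loss, n = 18 per arm; the noncentrality is 5.3 / (5.1 × √(2/18)) = 5.3 / 1.70 = 3.12. At two-sided alpha 0.027, power is 81.8% (normal) or 79.7% (noncentral t, 51 df), against the stated 80%. It has no bearing on the point here.

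**Assumptions.** The documents give neither the share p answering yes at baseline nor the correlation ρ between baseline severity and the participant's tendency to have fasciculation days. I take p from 0.75 to 0.95 and ρ from 0 to 0.5.

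**Step 1: how much a yes/no cut can lose.** Suppose one latent normal severity drives both the baseline report and the outcome. A cut at share p keeps a fraction c = φ(z_p)² / [p(1 − p)] of the R² of an ideal graded covariate.

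- p = 0.75: c = 0.318² / 0.1875 = 0.54
- p = 0.95: c = 0.103² / 0.0475 = 0.22

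Residual variance with the yes/no item, relative to the ideal graded one, is (1 − cρ²) / (1 − ρ²):

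| p | ρ = 0.3 | ρ = 0.5 |
|---|---|---|
| 0.75 | 1.05 | 1.15 |
| 0.95 | 1.08 | 1.26 |

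At p = 0.95 and ρ = 0.5 the interval is √1.26 = 1.12 times as wide. On the same assumption about 60 × 0.05 = 3 participants answer no, and an arm of 20 has none of them with probability 0.95²⁰ = 0.36. These ratios are upper bounds, because the real items are not an ideal measure of day frequency.

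**Step 2: let severity and day frequency differ.** None of the items in SAP 3.3.7 counts days. A fairer simulation therefore lets severity among those answering yes have its own correlation with day frequency. Set-up: 20 per arm, 28 on-drug diary days, logit mean 1, between-patient SD 2, log odds ratio -1.3, participant-level empirical logits in a linear model, pooled active versus placebo, two-sided alpha 0.05, 3,000 runs. The Monte Carlo standard error of one power value is about √(0.63 × 0.37 / 3000) = 0.9 points.

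*Replacing* any/none by the grade (any/none item correlated 0.5 with the outcome):

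| Share yes | Severity correlation | Any/none | Grade instead | Change (points) |
|---|---|---|---|---|
| 90% | 0.3 | 62.8% | 65.2% | +2.4 |
| 90% | 0.1 | 63.1% | 61.6% | -1.5 |
| 90% | 0 | 63.2% | 60.4% | -2.8 |
| 75% | 0.3 | 64.5% | 66.3% | +1.8 |
| 75% | 0.1 | 66.2% | 65.8% | -0.4 |
| 75% | 0 | 64.8% | 62.3% | -2.5 |

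*Adding* the grade beside the any/none item, over 75-95% answering yes:

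| Severity correlation | Change in power against any/none alone |
|---|---|
| 0 | loss of at most about 1 point |
| 0.3 | gain of about 1-3 points |
| 0.5 | gain of about 4-8 points |

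Replacement can lose what the any/none item already provides. Addition keeps it and risks almost nothing.

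**The case against.** The strongest case against is that this is a preference about efficiency on one endpoint listed as exploratory, and that its size is not in the documents. Much of that stands.

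- **Prevalence.** A reader might infer that almost every ALS patient will answer yes, because Protocol 2.1.1 names as essential features "progressive signs and symptoms of lower motor neuron dysfunction (atrophy, cramps, and fasciculations". That is a list of clinical signs, not a rate of self-report over 14 days. Eligibility (Protocol 5.2) does not require fasciculations. The same list includes cramps, which Protocol 2.1.3.1 puts at over 75% of patients, so being listed does not make an item near-constant.
- **Coding.** Yes/no is an inference. SAP 3.7.3 gives no scale, the response options are not in the documents, and SAP 3.7.5 speaks of baseline fasciculation frequency although SAP 3.3.7 lists no such item. This is a reason to define the covariate.
- **Data discarded.** A reader might say that the graded data are thrown away. They are not: SAP 3.6 and 3.7.5 use baseline fasciculation data. The omission is from this model only.
- **Large gains.** If the grade is simulated as an ordered cut of the same latent variable that generates the day counts, gains reach 18 points at correlation 0.7. That set-up guarantees that the grade wins. Once the two are separated, a straight swap can lose up to about 3 points. This objection defeats replacement, but not addition.
- **Other precision.** The diary runs to Week 8, and the planned model uses weekly repeated data. The simulation uses neither, so it only approximates the planned analysis.

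**Conclusion.** The point holds as a modest, low-cost improvement. On the natural reading, the model adjusts for a yes/no item while baseline items that parallel the diary grade are left out. Under the stated assumptions, adding the grade is worth about 1-3 points of power at severity correlation 0.3 and about 4-8 at 0.5, and costs at most about 1 point at correlation zero. Where the trial lies in that range depends on two quantities that the documents do not supply.

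The documents do not support reading this as bias, as an invalid comparison or as a threat to the primary result. Randomization protects the comparison under either covariate. SAP 2.2 includes fasciculations in a secondary objective, but SAP 3.2.2 lists the endpoint as exploratory, and the primary RMT analysis is untouched.

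**What to change.** In SAP 3.7.3:

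1. State how the 14-day baseline fasciculation item is coded, and keep it in the model.
2. Add a second fixed effect: a baseline 14-day grade on the diary's 0-3 scale, entered as a linear score. Patients with no fasciculations score 0; the exertion/rest and interference items assign grades 1 to 3.
3. Write the derivation into the SAP before unblinding, including which interference responses count as substantial and how incomplete baseline answers are graded.

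The cost is a sentence or two of text, one derived variable from data already collected, one degree of freedom, and at most about 1 point of power if the grade proves unrelated to day frequency. No new data are needed.

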3.7.4 Subgroup Analyses

Differences in treatment efficacy will be explored in several pre-defined subgroups: baseline RMT (median split) and baseline riluzole use (yes vs. no). Subgroup specific estimates will be obtained by including subgroup, subgroup \times visit, and subgroup \times treatment \times post-baseline visit terms to models for primary and secondary pharmacodynamic outcomes using the mITT sample.

3.7.5 Associations between Muscle Symptoms and TTNCS Parameters

Associations between frequency and intensity of muscle cramps and fasciculations and TTNCS parameters will be assessed at baseline and longitudinally and with respect to response to mexiletine. At baseline, Spearman correlations will be calculated between measures of muscle cramp frequency and pain and fasciculation frequency and interference and TTNCS parameters. Longitudinally, Spearman correlations will be calculated between rates of change in muscle cramp frequency and pain and fasciculation frequency and interference and rates of change in TTNCS parameters. To test whether any reduction in frequency and intensity of muscle cramps and fasciculations resulting from treatment with mexiletine is associated with changes in TTNCS parameters, we will estimate whether 4-week changes in TTNCS parameters mediate any effect of mexiletine on 4-week changes in muscle cramp frequency and pain and fasciculation frequency and interference using a causal mediation framework for analysis (Valeri et al. 2013).

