3.2. Secondary

Secondary pharmacodynamics outcome measures will include effects on motor evoked potential (MEP) amplitude (as a % of CMAP) and cortical silent period (CSP) measured by single pulse TMS, and SICI measured by dual pulse TMS, as additional pharmacodynamic markers of cortical hyperexcitability, prior to and following treatment with mexiletine or placebo. Additionally, as a pharmacodynamic marker of peripheral motor nerve axonal hyperexcitability, threshold tracking nerve conduction studies (TTNCS) will be performed to assess strength duration time constant and recovery cycle analysis. Safety and tolerability and determination of mexiletine concentrations in blood at the time of each of the four TMS studies will also be assessed. Additionally, the effect on frequency and severity of muscle cramps and fasciculations will be assessed using a daily muscle cramps/fasciculations diary from the Baseline Visit through the Week 8 Visit and using an assessment form at the Baseline Visit. ALS Functional Rating Scale-Revised (ALSFRS-R) and slow vital capacity (SVC) will be obtained at Screening, Pre-Dose Baseline, Week 4, and Week 8 or the Final Safety Visit, if applicable as exploratory outcomes.

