2.1 Overview

This is a multicenter, double-blind, placebo-controlled, three-arm, parallel-group, phase 2 randomized controlled trial to examine the effect of two dosages of mexiletine on neuronal excitability in ALS patients. Trial participation includes a screening visit, randomization to placebo, 300 mg/day oral mexiletine, or 600 mg/day oral mexiletine, 4 weeks of follow-up on study drug, and 4 weeks of follow-up after last dose of study drug. The trial is registered at Clinicaltrials.gov as study NCT02781454 (see <https://clinicaltrials.gov/ct2/show/NCT02781454>).

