2.6 Treatment Administration

Study drug will be orally self-administered from 2 bottles containing either 150 mg capsules of mexiletine or placebo capsules matched for size, color, and presentation. All participants will take one capsule for bottle #1 at their baseline visit (day 1) and on the morning of day 2, one capsule from bottle #1 BID from day 3 until their week 4 visit, one capsule from bottle #2 on the morning of days 5 and 6, and one capsule from bottle #2 BID from day 7 until their week 4 visit.

In the placebo arm, bottles #1 and #2 will contain placebo capsules, and the dosage of mexiletine will be 0 mg/day throughout their participation. In the 300 mg/day arm, bottle #1 will contain 150 mg capsules of mexiletine and bottle #2 will contain placebo. Dosage of mexiletine will be titrated as follows: 150 mg at their baseline visit, 150 mg on the morning of day 2, and 150 mg BID (300 mg/day) from day 3 until their week 4 visit. In the 600 mg/day arm, bottles #1 and #2 will contain 150 mg capsules of mexiletine. Dosage of mexiletine will be titrated as follows: 150 mg at their baseline visit, 150 mg on the morning of day 2, 150 mg BID (300 mg/day) on days 3 and 4, 300 mg QAM and 150 mg QPM (450 mg/day) on days 5 and 6, and 300 mg BID (600 mg/day) from day 7 until their week 4 visit.

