3.3.6 Cramping

Frequency of muscle cramping and maximum pain from muscle cramping is collected at baseline by retrospective report of the prior 7 and 30-day intervals. Prospective muscle cramping and pain from muscle cramping is recorded starting at baseline by participants in daily diaries and then summarized as weekly summaries of total number of cramps experienced and maximum and average daily maximum pain from muscle cramping.

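### The rates of change correlated in SAP 3.7.5 are undefined, and slopes fitted across treatment and washout can hide or reverse a drug-driven link between cramp relief and nerve excitability

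*SAP*

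**What the plan says.** SAP 3.7.5 describes three analyses: correlations at baseline, longitudinal correlations, and mediation of the drug response. For the second it says: "Longitudinally, Spearman correlations will be calculated between rates of change in muscle cramp frequency and pain", continues with fasciculations, and pairs these with rates of change in TTNCS parameters. It does not give the interval, the way a participant's rate is obtained, or whether arms are combined. The third asks whether "4-week changes in TTNCS parameters mediate any effect of mexiletine on 4-week changes in muscle cramp frequency and pain".

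The data behind these analyses are as follows.

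- **Diary.** SAP 3.3.6: "Prospective muscle cramping and pain from muscle cramping is recorded starting at baseline by participants in daily diaries". Protocol 3.2 describes a "daily muscle cramps/fasciculations diary from the Baseline Visit through the Week 8 Visit". The first dose is taken at that same Baseline Visit. The only pre-drug symptom data are recall: 7 and 30 days for cramps, 14 days for fasciculations (SAP 3.3.6 and 3.3.7).
- **Treatment.** SAP 2.1 plans "4 weeks of follow-up on study drug, and 4 weeks of follow-up after last dose of study drug". Under SAP 2.6 the lower-dose arm takes "150 mg BID (300 mg/day) from day 3 until their week 4 visit" and the higher-dose arm "300 mg BID (600 mg/day) from day 7 until their week 4 visit".
- **TTNCS.** Screening, pre-dose Baseline, Week 4 and Week 8 (SAP 2.8).
- **Slopes.** SAP 3.7.1 defines a participant-specific slope per month from treatment initiation, in a model of all four visits. SAP 3.7.3 carries that model to the continuous secondary endpoints, which include TTNCS. Protocol 13.7 also puts participant-specific slopes in the weekly cramp model.
- **Recalled baseline.** For the symptom models SAP 3.7.3 says: "Because diary data are only collected after baseline, fixed effects in the model will include treatment group", then adds post-baseline week and the recalled baseline. Recall is therefore a covariate there.

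**The concern.** A rate of change is a sensible summary when a quantity drifts steadily. Here the expected drug effect switches on near the start of the diary and off halfway through it. A straight line through such a pattern does not measure the drug effect. The two variables are also sampled differently: TTNCS has a pre-drug value and the diary has none. The same on-drug benefit can therefore enter the two slopes with different weights and opposite signs.

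Protocol 4.1 presents TTNCS as a potential marker for the therapeutic effect of mexiletine on cramps and fasciculations. A near-zero or negative longitudinal correlation would be read as evidence against that idea, even if it came only from the choice of window. Because the window is open, the sign of the result could depend on a decision made during analysis.

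**Working it through.** The plan gives no figure for this analysis, so there is none to reproduce. Both measures are coded so that a lower value means less excitability or fewer cramps, and the drug effect is −1 while on drug.

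**Slope formula.** The least-squares slope is Σ wᵢyᵢ, with wᵢ = (tᵢ − t̄)/Σ(tⱼ − t̄)².

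**TTNCS, screening included.** Take months −0.5, 0, 1, 2; the −0.5 is an assumed placement within the 21-day screening limit. Then t̄ = 0.625 and the sum of squares is 1.266 + 0.391 + 0.141 + 1.891 = 3.688. The weights are −0.305, −0.169, +0.102 and +0.373. Only Week 4 is on drug, so a shift of −1 gives a slope of −0.10 per month.

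**TTNCS from Baseline.** At months 0, 1, 2 the weights are −0.5, 0, +0.5, so the on-drug value drops out. At days 0, 29, 56 the slope is −0.01, with a range of −0.07 to +0.01 over the visit windows.

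**Diary, Weeks 1–8.** t̄ = 4.5 and the sum of squares is 42. With −1 in Weeks 1–4 and 0 afterwards, the slope is (3.5 + 2.5 + 1.5 + 0.5)/42 = 8/42 = +0.19 per week, or +0.76 per four weeks.

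**Diary, allowing for titration.** Assume the effect is proportional to dose.

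- 300 mg/day: the Week 1 average is (2×0.5 + 5×1)/7 = 6/7. The slope is (3.5×6/7 + 4.5)/42 = 0.179 per week, or +0.71 per four weeks.
- 600 mg/day: the Week 1 average is (2×0.25 + 2×0.5 + 2×0.75 + 1)/7 = 4/7. The slope is (3.5×4/7 + 4.5)/42 = 0.155 per week, or +0.62 per four weeks.

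Adding recalled baseline as an extra time point reduces the diary slope to between +0.22 and +0.37 per month. It stays positive.

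**Simulation.** The sample is 60 participants, 20 per arm (SAP 2.4), with 500 runs per setting. The rest is assumed: each participant's drug effect is the same on both measures, with mean 0.5 (300 mg) and 1.0 (600 mg) and SD 0.5; onset and offset are immediate; natural slopes are uncorrelated. The true link is therefore positive and driven only by the drug. Mean Spearman correlations:

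| Residual SD; SD of natural slopes per month | Full-interval slopes, with screening | Full-interval slopes, without screening | Treatment-period changes |
|---|---|---|---|
| 0.2; 0 | −0.45 | −0.05 | +0.81 |
| 0.4; 0.1 | −0.19 | −0.02 | +0.56 |
| 0.4; 0.3 | −0.11 | −0.01 | +0.50 |

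Treatment-period changes here are TTNCS from pre-treatment to Week 4, against diary Weeks 1–4 minus recalled baseline. A matched on-minus-off contrast (TTNCS Week 4 minus Week 8, diary on-drug minus washout) gave +0.29 to +0.73 in separate runs with 18 per arm and assumed noise SD of 0.3 to 0.8.

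**Arms.** With no within-participant link and both change scores shifted by an assumed 0.8 to 1.5 SD in the active arms, a pooled Spearman test was significant in 14% to 74% of simulated trials across two sets of runs. Adjusted for arm, the figure was 4% to 6%. These percentages describe change scores. They do not describe full-interval slopes, which carry little of the TTNCS shift.

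**The case against.** The strongest reply is that SAP 3.7.5 does not say the rate covers eight weeks. That is correct. A rate confined to the treatment period avoids the reversal: diary slopes within Weeks 1–4 gave +0.47, +0.22 and +0.21 in the three settings, which is attenuated but correctly signed. The full-interval reading rests on 3.7.1 defining the only slope in the SAP, which makes it the natural reading but not a stated one.

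Four further replies also stand in part.

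- **The link need not come from the drug.** If natural slopes of symptoms and TTNCS correlate at 0.7, full-interval slopes with screening give +0.18 to +0.45. Co-progression, including in placebo, keeps its sign.
- **The effect may be slow.** If cramp relief builds and fades with a 4-week time constant, the diary slope becomes slightly negative (−0.05 to −0.07) and is no longer reversed. The half-life of 10 to 12 hours in Protocol 2.2.1.1 makes fast offset plausible for plasma drug, but does not settle how quickly symptoms return.
- **Model-based slopes shrink.** Slopes predicted from a mixed model gave about −0.07 to −0.08 (60 runs per setting, several with convergence warnings). That is closer to no association than to a reversal.
- **The drug-response question has its own analysis.** The mediation analysis uses 4-week changes, which washout does not affect.

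A reader might infer three stronger things: that the longitudinal result will come out backwards, that arms will be pooled without adjustment, and that mediation will subtract a recalled count from a diary count. The documents support none of these. The first needs a particular window and a fast, reversible effect. On the other two SAP 3.7.5 is silent, and 3.7.3 already treats recall as a covariate in the symptom models.

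**Conclusion.** The point holds in limited form, and it is more than a missing detail. Applying the SAP's own slope definition to an on/off design gives a drug-driven association that is attenuated to about zero or turned negative (mean −0.45 to −0.01 in the settings above), while contrasts over the treatment period recover it (+0.50 to +0.81).

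The slope weights follow from the visit and diary times, apart from the assumed screening time and the dose-proportional titration effect. The correlations rest on assumed effect sizes, noise, and immediate onset and offset, so they show direction and mechanism and do not forecast this trial's result.

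The consequence is confined to an ancillary association. SAP 3.2.2 lists cramping and fasciculations as exploratory clinical endpoints. The separate cramp efficacy model in 3.7.3 and the primary resting motor threshold analysis do not depend on this one.

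**What to change.** Reword SAP 3.7.5 before unblinding.

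1. **Replace rates of change with contrasts over matched windows.** Either pair TTNCS Week 4 minus Week 8 with on-drug minus washout diary symptoms, or pair the TTNCS change from pre-treatment to Week 4 with on-drug diary symptoms adjusted for recalled baseline. Name one as the main version. Say which diary days count as on drug, since Week 1 includes titration and the Week 4 Visit may fall on Days 29 to 32 with the last dose the night before (Protocol 8.1.5).
2. **Adjust for randomised arm.** Use a partial Spearman correlation, or compute it within arm. This matters more once contrasts are used, because they carry the whole drug effect and a shift in both variables could by itself create a correlation.
3. **Specify the mediation outcome.** Use on-drug diary symptoms as the outcome with recalled baseline as a covariate, in line with SAP 3.7.3.
4. **If co-progression is also of interest,** state it as a separate question with its own defined slope.

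No new data are needed. The on-minus-off contrast assumes that the effect largely reverses during washout, and the alternative leans on recalled symptoms. Adjusting for arm costs a little precision; within-arm correlations would rest on about 20 participants each.
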